3.3 FTC Qualitative Plasma Concentration as an Adherence Marker

Adherence to prescribed treatment can be difficult to assess. One objective way to measure recent adherence is to measure plasma drug concentrations. FTC concentrations in plasma remain detectable throughout the dosing interval. Specifically, trough concentrations of FTC are approximately 60 – 70 ng/mL, and range from 10 – 300 ng/mL between subjects [23, 24]. Peak concentrations are approximately 1300 – 1800 ng/mL, and range from 600 to 2500 ng/mL. While many factors contribute to variability in plasma concentrations, such as drug-drug interactions and genetic differences in absorption and excretion, completely undetectable plasma concentrations of FTC are physiologically implausible for patients who are adherent with their regimen. Even with the sources of variability noted above, undetectable concentrations (< 1 ng/mL) would be 60 to over 1000 times less than the expected concentration depending on the time post-dose, and can be justifiably assumed to represent missed doses rather than pharmacokinetic variability. We plan for 400 subjects and in total will have 3467 levels (an average of 8.6 per person). Samples will be stored at each study visit (weeks 4, 12 and every 12 weeks thereafter).

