6.2.3 On-Study Evaluations

After counseling, laboratory testing and randomization, participants will receive sufficient TDF/FTC study medication to last until the next scheduled visit (either 4 or 12 weeks) through the investigational pharmacy. Medication renewals will not be available if a subject misses a scheduled appointment. An informational pamphlet on TDF/FTC will be provided that will summarize the label package insert information for patients (in English or Spanish) with changes made to tailor the information for someone that is not HIV infected. Participants will be directed to take one pill once a day at a convenient routine time. If there are missed doses, participants will be told to take the next scheduled dose on time and not to take any additional pills to catch up. Bottles with any remaining missed doses will be returned to the pharmacy at the time of medication renewal and the number of untaken doses will be recorded. At each clinic visit, TDF/FTC medication adherence will be

reviewed by the clinician, adverse events will be queried and adherence and barriers to adherence will be discussed. All subjects will receive episodic adherence counseling within the confines of routine clinic visit. Each clinic visit will also include blood draw for calculated GFR (serum creatinine) and plasma FTC drug levels, and HIV testing. STI testing including NAT screening for GC and chlamydia from throat and rectal swabs and from urine and RPR from blood will be done at week 0 and every 24 weeks thereafter.

Adherence and Behavioral Assessments

We will measure adherence using the ACTG medication adherence questionnaire [25]. At each follow-up visit, the ACTG four-day questionnaire will be administered using the web-based data capture system. The instrument tracks the number of doses skipped over the past four days and reasons why medications may have been skipped. In addition, we will ask their ability to adhere by Likert scale and use the Visual Analog Scale (VAS), which appears as an ordinal scale representing the percent of medication taken relative to that which has been prescribed over the past 4 weeks. Subjects are presented with a line anchored at 0% and 100% and are asked to mark a line on the scale indicating their own PrEP adherence [26].

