6.3.10 T-cell counts and Virology tests

Plasma HIV-1 RNA

An HIV-1 RNA viral load will be performed at the site's local laboratory within 7 days of a new positive antibody test or NAT.

An HIV drug resistance test should be performed with detectable viral load of greater than 500 copies/mL.

CD4 T-cell enumeration will be performed to obtain absolute CD4+/CD8+ count and percentages within 7 days of new HIV diagnosis.

6.3.11 *Stored Plasma and other specimens*

Stored plasma will be collected at day 0, at all visits and with any new HIV diagnosis.

*Specimens will be stored at the site's local laboratory and batched shipped to the central laboratory (UCSD) after completion of the study.

6.3.12 *Pharmacokinetic Studies*

At each visit, record the time and date of the last 3 doses of TDF/FTC medication in the CRF. Dried blood spots will be stored at -80 at each visit beginning at Week 12 for possible future use for plasma and intracellular TFV and FTC pharmacology.

6.3.13 *Questionnaires*

At each visit, the subject should complete the self-reported questionnaires.

6.3.14 *Rectal swabs*

At day 0 and at one additional time point on or after Week 48, all subjects will have a rectal swab stored for possible future studies of the gut microbiome. These tests will be done in retrospect and not available for the subjects.

6.3.15 At day 0, all subjects will have blood stored for future use to examine host DNA. Subjects will sign a consent that informs them of the storage of material for possible host genomic testing.

6.3.16 Participants will be asked to recall food items eaten over the last 3 days at the week 36 visit. The calculator used in the ACTG 5280 study, which is adopted from the USDA database, will be used to quantify vitamin D and calcium intake (see Appendix VI).

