10.0 PHARMACOLOGY PLAN

10.1 Sample Assay Methods

FTC concentrations will be measured in the Pediatric Clinical Pharmacology Laboratory of the University of California, San Diego by a validated, Liquid Chromatography-Mass Spectrometry (LC-MS) method. The laboratory is registered with the ACTG Quality Assurance/Quality Control proficiency testing program [27] and successfully completes proficiency testing for the accuracy and precision of the FTC assay every 6 months. Inter-assay variability is less than 6% for low, middle and high controls. The lower limit of detection of FTC is approximately 1 ng/mL (the lower limit of quantitation is 11.8 ng/mL). For qualitative assays, unknown samples will be measured in the presence of internal standard to determine if the FTC ion peak is present (≥ 1 ng/mL) or absent (< 1 ng/mL). Stored plasma samples will be bulk testing of qualitative presence of FTC at the end of follow-up. Additional pharmacology analyses will be done in retrospect and the specific analysis will be included in the SAP prior to data log and sample testing.

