The primary adherence endpoint will be a binary endpoint (Yes/No) based on DBS samples from two visits (week 12 visit and the last on-drug visit over the 48 weeks). Both visits should have a detectable TFV-DP level >719 fmol/punch (consistent with taking four or more doses per week) to be considered adherent. If the last on-drug visit was at week 12 (i.e. the subject had only one DBS sample), adherence will only be determined by that sample. If a subject discontinued study before week 12 (i.e. had no DBS samples at all), the subject will be considered non-adherent.

Additional Secondary Adherence Endpoints

- Self-reported Adherence: a binary composite endpoint of continued on PrEP and $\geq 90\%$ self-reported adherence to TDF/FTC over 48 weeks. The endpoint will be defined yes if 14 or 15 out of 15 days were reported 'adherent' on the 3-day recall on the clinical assessment form collected at w4, w12, w24, w36, and w48. Note if a subject discontinued the study or missed any visits before w48, those visits will be considered not adherent in the calculation.
- a continuous version of the self-reported adherence measure: defined as percent days that were reported adherent based on the clinical assessment form. In the case where the adherence measure is missing (either due to the subject discontinued PrEP, or missed visit, or other reasons), two approaches will be applied.
 - treat the missing as 'not adherent'. This assumes the worst case (i.e. assume all the missing is related to adherence).
 - ignore the missing. This assumes the best case (i.e. assume all the missing is not related to adherence).
- FTC Adherence: a binary endpoint of having four of four detectable qualitative FTC plasma concentrations (measured at w12, w24, w36, and w48) over 48 weeks. Detectable FTC is defined as a quantitative level of ≥ 0.35 ug/ml consistent with taking a dose in past 24 hours. Note missing will be treated as not detectable.
- Similar outcome as the primary endpoint where we will use the cut-off of ≥ 1246 fmol/punch consistent with taking seven doses per week.
- Proportion of subjects on PrEP at week 48.

Descriptive Analysis

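### The SAP's FTC endpoint sets 'detectable' at 350 ng/mL, above the protocol's whole trough range, so an adherent participant drawn at trough is coded a failure

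*SAP*

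**What the plan says.** SAP section 6 (Additional Secondary Adherence Endpoints, FTC Adherence) defines a yes/no endpoint. Plasma FTC must be detectable at all four visits (weeks 12, 24, 36 and 48), and a missing result counts as not detectable. The endpoint's name says qualitative, but the next sentence defines detectable as a quantitative level of at least "0.35 ug/ml consistent with taking a dose in past 24 hours".

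Protocol 3.3 gives typical troughs of about 60–70 ng/mL that "range from 10 – 300 ng/mL between subjects", and typical peaks of about 1300–1800 ng/mL (range 600–2500). It says FTC stays detectable through the whole dosing interval. It also argues that undetectable levels, below 1 ng/mL, "can be justifiably assumed to represent missed doses rather than pharmacokinetic variability".

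Protocol 10.1 describes the qualitative assay, whose purpose is to "determine if the FTC ion peak is present", with the line at 1 ng/mL; "the lower limit of quantitation is 11.8 ng/mL". It plans bulk qualitative testing of stored plasma at the end of follow-up. For additional pharmacology analyses it says that "the specific analysis will be included in the SAP prior to data log and sample testing".

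On timing, Protocol 6.2.3 says: "Participants will be directed to take one pill once a day at a convenient routine time". Protocol 6.3.12 asks sites to "record the time and date of the last 3 doses of TDF/FTC medication in the CRF". Neither document ties the blood draw to the dose.

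**The concern.** The protocol's case for plasma FTC as an adherence marker runs in one direction: a level below 1 ng/mL is implausible in someone taking the drug daily, so it points to missed doses. The SAP's binary coding gives the same adverse result to every level below 350 ng/mL. That band includes every trough the protocol gives.

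The SAP's stated rationale supports only the opposite inference. A level of 350 ng/mL or more suggests a recent dose. A lower level does not show that no dose was taken in the past 24 hours, because the protocol's own end-of-interval levels all lie below the cut-off.

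Participants choose their dosing time and all four visits must pass, so one draw late enough in the interval turns an adherent participant into a failure. The endpoint then mixes pill-taking with the clock time of the visit, and a reader of the result could not separate the two.

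**Working it through.** **Inputs**
- Cut-off 0.35 ug/ml (SAP 6).
- Trough 60–70 ng/mL, range 10–300; peak 1300–1800 ng/mL, range 600–2500 (Protocol 3.3).
- Presence line 1 ng/mL and quantitation limit 11.8 ng/mL (Protocol 10.1).
- One dose every 24 h.

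**1. The protocol's own figure.** Protocol 3.3 says an undetectable level lies 60 to over 1000 times below expectation. 60/1 = 60 at typical trough and 1300/1 = 1300 at typical peak, so the figure is reproduced. It refers to the 1 ng/mL line only.

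**2. The SAP cut-off on the same scale.** 0.35 ug/ml × 1000 = 350 ng/mL.
- Against the top of the trough range: 350/300 = 1.17.
- Against the typical trough: 350/70 = 5.0 and 350/60 = 5.8.
- Against the presence line: 350/1 = 350.

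**3. What follows with no kinetic model.** The highest stated trough (300) is below 350, so every trough in the range fails. The lowest stated peak (600) is above 350, so every peak passes. The same adherent participant can therefore pass or fail according to when blood is drawn. Under the 1 ng/mL rule even the lowest stated trough passes, at 10/1 = 10 times the line.

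**4. Illustration of timing (assumptions not in the documents).** Assume a peak at 2 h and a mono-exponential fall to the 24 h trough. Then k = ln(peak/trough)/22, and the time at which the level reaches c is 2 + ln(peak/c)/k. For peak 1300 and trough 60, k = ln(21.67)/22 = 0.1398 per hour, and the time to 350 is 2 + ln(3.714)/0.1398 = 11.4 h.

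| Peak / trough (ng/mL) | Falls below 350 at | Falls below 1 at |
|---|---|---|
| 1300 / 60 | 11.4 h | 53.3 h |
| 1300 / 70 | 11.9 h | 56.0 h |
| 1800 / 60 | 12.6 h | 50.5 h |
| 1800 / 70 | 13.1 h | 52.8 h |

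Moving the assumed peak to 1 h or 3 h changes the 350 ng/mL times to 10.8–12.6 h or 12.0–13.6 h, and the 1 ng/mL times to 51.7–57.4 h or 49.3–54.5 h. In all these cases the whole number of 24 h intervals before the level falls below 1 ng/mL is 2, so up to two missed daily doses could still pass the presence rule.

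**5. Four visits.** If an adherent participant passed each visit independently with an assumed probability of 0.95, 0.90, 0.75 or 0.50, the chance of passing all four would be its fourth power: 0.81, 0.66, 0.32 or 0.06. The documents give no per-visit probability, and visits are unlikely to be independent in people with fixed routines. This shows only how strict the rule is.

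**The case against.** The SAP is the controlling document. Protocol 9.0 gives it precedence over the protocol's statistical section, and Protocol 10.1 leaves additional pharmacology analyses to it. The SAP states its number and what the number is meant to indicate. It also uses 'detectable' for the TFV-DP primary with a cut-off of 719 fmol/punch, so the word simply means above a stated level, and an analyst would not be in doubt. This largely stands as far as wording goes, and I would not press the label alone. It does not answer the substance. Precedence settles which rule is applied, not what a failed sample means, and Protocol 9.0 also expects the SAP to attend to changes of substance. The SAP neither mentions the move from 1 to 350 ng/mL nor squares it with the troughs in Protocol 3.3.

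Several stronger readings are tempting, and the documents do not support them:
- *That the endpoint understates adherence in both arms.* Late draws give false failures, but someone who misses most doses and takes one shortly before each visit passes. Neither draw times nor dosing patterns are given, so the net direction is unknown.
- *That the comparison of arms is biased.* Randomisation is 1:1 within site and nothing makes draw time depend on arm. Reminder times in the iTAB arm are set individually, but no data link them to draw times.
- *That the by-visit FTC tables repeat the problem.* SAP 6, Descriptive Analysis, does not say which FTC cut-off they use, and summaries of continuous levels are a possible reading.
- *That the presence rule could pass a very long run of missed doses.* That needs the lowest peak (600) paired with the highest trough (300), an implied half-life of 22 h against about 4.5–5.2 h at typical values. Nothing supports that pairing.
- *That 0.35 ug/ml is a slip of units.* The documents cannot show whether it is.

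**Conclusion.** The concern holds for the meaning of a failed sample. By the protocol's own figures, the SAP rule classes an adherent participant drawn at trough as not detectable, and one such visit decides the endpoint. This rests only on a unit conversion and a comparison with the stated trough range. How early in the interval failures begin (about 11–13 h at typical values) rests on the assumed decay curve. How many samples are affected depends on draw times that the documents do not give. The error can run in both directions, and its effect on the difference between arms cannot be determined. One secondary endpoint is affected; the TFV-DP primary and the 1246 fmol/punch secondary are not. It should be fixed, because the rule as written misclassifies and the remedy is cheap.

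**What to change.** Reconcile SAP 6 with Protocol 3.3 and 10.1, and report two measures under two names:
1. The four-visit detectable endpoint by the protocol's qualitative rule (ion peak present, at least 1 ng/mL).
2. The proportion at or above 0.35 ug/ml, by visit and arm, labelled a recent-dose marker with the source of the cut-off stated. A lower level should not be read on its own as a missed dose. Optionally, tabulate it by hours since the last recorded dose (Protocol 6.3.12) if draw times are available; the documents do not say that they are recorded.

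The downside should be stated in the SAP: the presence rule is less specific. Under the assumed model with a 2 h peak and typical values, levels stay above 1 ng/mL for about 50–56 h, so up to two missed doses can pass. That is why both measures are needed rather than a swap of cut-offs.

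The cost is a few SAP sentences and some table rows. Because 1 ng/mL lies below the 11.8 ng/mL quantitation limit, the first measure needs the qualitative reading. Protocol 10.1 already plans that reading on stored plasma. If only quantitative values were reported, it means reading at most 400 × 4 = 1,600 samples again.

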¹ Pre: attitudes toward safe sex, disclosure, access to care, social support, texting ability, Kalichman sexual compulsivity; Post: satisfaction with iTAB; Pre/Post: HIV literacy, stigma and disclosure, AUDIT, DAST-10 ² includes: risk behavior, adherence assessments, intention to adhere, PHQ9, SCID substance use screen ³ Perform if HIV+ ⁴ Any time history or symptoms suggest potential HIV or STI, check with study MD for appropriate test ⁵ Subjects may have an interim visit if past window of scheduled visit, next visit should be back to regular schedule ⁶ To be performed at week 36 only ⁷ Performed only once on or after Week 48 coinciding with STI screening (Week 48, 72, or 96)											

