3.2 Secondary Objectives

1. To determine factors associated with poor adherence/lost to PrEP in study participants. Factors will include demographics, ongoing substance use, untreated mental illness, socioeconomic status, low health/HIV and system literacy, fear of disclosure and non-English language.
2. To determine the rate of HIV seroconversion in PrEP users and compare the iTAB to SoC arms for number of new infections as a proportion at 48 weeks and end of the study.
3. To measure acquisition of other sexually transmitted infections (STIs); the proportion of subjects with any new STI at any site will be compared between the iTAB to SoC arms at 48 weeks and end of the study.
4. To evaluate changes in risk behavior after initiation of PrEP (risk compensation) comparing baseline to subsequent visits for number of HIV positive/unknown status partners and any unprotected anal intercourse with an HIV positive/unknown status partner.
5. To evaluate the safety and tolerability of daily TDF/FTC given for PrEP including discontinuation for any adverse event, serious adverse events, and adverse events (grade 2 or higher).

4 Subject Disposition

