4.2 Evaluation of Premature Discontinuation from Study

Proportions of subjects prematurely discontinued the study will be compared between the study arms using Fisher's exact test. The numerator will be the number of subjects who marked other than 'complete the study' as the primary reason in the Termination form. The denominator will be the number of subjects who were randomized.

Time to premature discontinuation will be summarized overall, and by study arm using the method of Kaplan and Meier. The cumulative probability of premature discontinuation will be estimated overall and by arm, with 95% confidence interval. Log-rank test will compare time to premature discontinuation between randomized arms.

The survival indicator will be defined (1=early discontinued the study; 0=completed the study). The event time and censoring time will be defined from the baseline date to the termination date indicated in the Termination form.

5 Evaluation of Demographics and Baseline Characteristics

Tables will summarize the study population at baseline, overall and by study arm. Descriptive statistics will be presented as N, mean, standard deviation, minimum, 25th Q, median, 75th Q, maximum for continuous variables; frequency tables (row, column percentages) will be used for categorical variables. Statistical comparisons will be performed between randomized arms using Wilcoxon Rank Sum Test (for continuous variables) or Fisher's exact test (for categorical variables). The following variables will be examined at baseline:

- Age
- Race/Ethnicity (White, Black, Hispanic, Other)
- Education
- Household average monthly income
- Inclusion criteria
- STI status
- Language (English vs Other)
- Substance use (SCID screen)
 - Any drug use reported other than alcohol and marijuana
 - Meth use
- AUDIT score
- DAST score
- Sexual Compulsivity Score (SCS)
- HIV literacy score

6 Evaluation of Primary Objective

The primary objective of the study is to compare the adherence to PrEP during the 48-week study period between the iTAB intervention group and the SoC group.

The primary analysis will be conducted on the modified intent-to-treat (mITT) population (i.e. randomized subjects who started PrEP).

Primary Adherence Endpoint

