Descriptive analysis will look at self-reported adherence, FTC adherence and TFV-DP adherence measures by visit. Continuous outcome will be summarized with N, min, Q1, median, Q3, and max, by study arm and overall. Binary endpoint will be summarized with frequency tables, by study arm and overall. Wilcoxon rank sum test will be used for comparison for continuous outcome; Fisher's exact test will be used for binary outcome.

Statistical Inference

A logistic regression model will be performed to compare the adherence over 48 weeks between the two groups. The model will include baseline factors (refer to the baseline variable list) as covariates if they are found unbalanced between the study arms (with $p < 0.1$) and also univariately associated with the outcome ($p < 0.15$). Interactions between each of the covariates and study arm will also be assessed individually. Significant interactions ($p < 0.05$) will be included in the final model.

7 Evaluation of Secondary Objectives

7.1 Secondary Objective 1

To determine factors associated with poor adherence/lost to PrEP in study participants. Factors will include demographics, ongoing substance use, untreated mental illness, socioeconomic status, low health/HIV and system literacy, fear of disclosure and non-English language.

This objective will be assessed along with the primary objective analysis. The final primary multivariable model will be able to answer this question.

7.2 Secondary Objective 2

To determine the rate of HIV seroconversion in PrEP users and compare the iTAB to SoC arms for number of new infections as a proportion at 48 weeks and end of the study.

Number and proportion of subjects with HIV-seroconversion at 48 weeks will be summarized by study arm and overall. Fisher's exact test will be used for comparison. Same analysis will also look at the rate of seroconversion during the whole study period.

7.3 Secondary Objective 3

To measure acquisition of other sexually transmitted infections (STIs); the proportion of subjects with any new STI at any site will be compared between the iTAB to SoC arms at 48 weeks and end of the study.

Any new STI will be defined as positive results from Gonorrhea (GC) or Chlamydia (CT) at any site or positive syphilis RPR result with titer $>1:4$ based on the STI form collected after baseline visit.

Sensitivity analysis will also be performed looking at STI by testing as well as self-reported STI (outside diagnosis) based on the clinical assessment form.

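### SAP 7.1 relies on the primary model to identify factors for poor adherence, but that model's candidate list has no variable for mental illness or fear of disclosure and covers literacy only in part

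*SAP*

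**What the plan says.** SAP 3.2 and SAP 7.1 set out Secondary Objective 1 in the same terms: "Factors will include demographics, ongoing substance use, untreated mental illness, socioeconomic status, low health/HIV and system literacy, fear of disclosure and non-English language". SAP 7.1 gives the objective one analysis, the one done for the primary objective: "The final primary multivariable model will be able to answer this question".

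That model is described in SAP 6 under Statistical Inference: "The model will include baseline factors (refer to the baseline variable list) as covariates". A listed factor enters only if it differs between arms at p < 0.1 and is also associated with the outcome, one variable at a time, at p < 0.15.

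The list is in SAP 5, under the line "The following variables will be examined at baseline". It holds age, race/ethnicity, education, household income, inclusion criteria, STI status, language, two SCID drug-use items (any drug other than alcohol and marijuana; methamphetamine), AUDIT, DAST, sexual compulsivity and HIV literacy.

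The protocol collects more than this. Footnote 2 of the schedule in Protocol 6.1 describes the survey given from week 0: "includes: risk behavior, adherence assessments, intention to adhere, PHQ9, SCID substance use screen". Footnote 1 covers the pre/post assessments: "Pre/Post: HIV literacy, stigma and disclosure, AUDIT, DAST-10". Appendix II schedules PHQ9 at all visits, the Stigma and Disclosure survey at baseline, week 48 and end of study, and the Access to Care survey at baseline.

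Protocol 9.6.4 plans multivariable logistic regression for this question and names mental illness and fear of disclosure among the potential covariates. Protocol 9.0 says the SAP prevails where the two differ.

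**The concern.** A factor that is not a candidate for a model cannot be estimated by it. The SAP promises an answer on untreated mental illness and fear of disclosure from a model that has no variable for either. System literacy is in the same position, because the only literacy item on the list is the HIV literacy score.

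This gap is separate from the entry rule. If every variable in SAP 5 were forced into the model, these factors would still be absent. An analyst who follows the SAP would report nothing on them, and any PHQ9 or disclosure result added later would be post hoc.

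**Working it through.** The plan gives no figure on this point, so the main check is a comparison of the two lists.

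**Step 1. Factor groups in SAP 7.1 against the variables in SAP 5.**

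| Factor group | Variable in SAP 5 | Uncovered part: baseline source |
|---|---|---|
| Demographics | Age, race/ethnicity | – |
| Substance use | Two SCID items, AUDIT, DAST | – |
| Untreated mental illness | None | PHQ9 |
| Socioeconomic status | Education, income | – |
| Health/HIV and system literacy | HIV literacy score only | Access to Care survey, as a possible proxy |
| Fear of disclosure | None | Stigma and Disclosure survey |
| Language other than English | Language | – |

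Two of seven groups have no variable and one is partly covered. The other list entries (inclusion criteria, STI status, sexual compulsivity) do not fill the gaps.

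**Step 2. What the baseline sources measure (Appendix II).** PHQ9 asks about depressive symptoms over two weeks. It does not record treatment, and the documents define no variable for untreated illness. In the Stigma and Disclosure survey, items 1 to 5 are opinions about people with HIV and about gay people, while items 15 to 20 concern privacy and asking about HIV status. A total over all 20 items would therefore mix constructs. Access to Care is a set of check-all-that-apply lists. Some entries concern not knowing how to get care, and its fifth question covers fears of being found out. The documents do not call it a literacy measure and give no score for it.

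**Step 3. Would adding the scores to SAP 5 be enough?** Inputs: 200 per arm (Protocol 9.4), imbalance threshold 0.1 (SAP 6), Fisher's exact test for categorical baseline variables (SAP 5). Assumptions: all 400 are analyzed, site stratification is ignored, and prevalence is varied because the documents give none.

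For a binary factor present in m of 400 participants, the number i in one arm is hypergeometric under 1:1 randomization:

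P(pass) = sum of Hypergeometric(i; 400, m, 200) over all i for which Fisher's p < 0.1.

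| Assumed prevalence | P(pass the imbalance step) |
|---|---|
| 10% | 6.6% |
| 20% | 6.0% |
| 30% | 6.3% |
| 50% | 8.9% |

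For a continuous score the probability is close to the nominal 10%, so 10% serves as a ceiling. At that ceiling, with two added scores assumed independent, at least one passes with probability 1 − 0.9² = 19%, and both with 0.1² = 1%. These figures come before the association step. Among the 13 items already listed, at most about 13 × 0.1 = 1.3 would be expected to pass the imbalance step.

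So even a factor strongly related to adherence would stay out of the final model about nine times in ten, because imbalance between arms has nothing to do with how well a factor predicts adherence.

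**The case against.** The strongest reply is that the intent is already clear. SAP 3.2 and SAP 7.1 name both factors, Protocol 9.6.4 names them as potential covariates, and SAP precedence applies only where the documents differ. On the names they agree. This stands as far as it goes: a reader might infer that the SAP deliberately dropped these factors, and nothing in the documents supports that. But the two documents do differ on the model. Protocol 9.6.4 lists the named factors as covariates and adds unbalanced variables to them. SAP 6 admits only variables that are on its own list and unbalanced. The protocol therefore does not clearly rescue the analysis.

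A second reply is that the missing variables are a small part of a larger problem, the entry rule. Step 3 bears this out for the remedy: extending the list would leave the objective mostly unanswered. It does not remove the gap, which would remain with no rule at all.

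Third, a reader might infer that the two factors are measured directly and merely left out. They are not; the instruments are proxies, and the disclosure and access items need scoring rules that do not yet exist.

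Fourth, a reader might infer a definite loss of power, or confounded estimates for listed factors such as substance use. The documents give no prevalence or adherence by depression status from which to compute power. The listed factors would themselves usually be kept out of the model.

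Finally, the objective is secondary, without multiplicity control (Protocol 9.6.1), and no data are lost. That limits how serious the point is.

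**Conclusion.** The point holds as an internal inconsistency in the SAP. The model assigned to Secondary Objective 1 has no variable for two of the seven named factor groups and only partly covers a third, so the statement in SAP 7.1 that it can answer the question is wrong as written. This rests on the text of SAP 5, 6 and 7.1 and needs no numerical assumption. The figure of at most about 10% for passing the imbalance step assumes simple 1:1 randomization of 400; it affects the choice of remedy and not the finding.

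The consequence is confined to a secondary objective. The comparison of iTAB with standard of care is not affected, and the proxy data will be available. The SAP should be corrected before the factor analysis is run.

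**What to change.** In SAP 7.1, replace the reliance on the primary model with a separate prespecified multivariable logistic model for poor adherence, in line with Protocol 9.6.4, that includes all the named factors whether or not they differ between arms. State its outcome explicitly, because Protocol 9.2.3 defines poor adherence by self-report or stopping drug, while the primary endpoint in SAP 6 is based on TFV-DP.

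Map each factor to a baseline instrument and a scoring rule:

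- mental illness: PHQ9 total;
- fear of disclosure: a subscore from the privacy and disclosure items of the Stigma and Disclosure survey, with the do-not-know and prefer-not-to-answer codes (8 and 9) treated as missing;
- system literacy: selected Access to Care items, chosen in advance.

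Say that these are proxies and that PHQ9 does not establish untreated illness. Add the new scores to the SAP 5 baseline table, and state that this does not make them candidates for the primary model.

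The cost is a few derived scores, at least two of which need new scoring definitions, and one more secondary model. No new data collection is needed, and the primary comparison does not change.
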